8.3.5.2. Exposure During Breastfeeding

An exposure during breastfeeding occurs if:

- A female participant is found to be breastfeeding while receiving or after discontinuing study intervention.
- A female is found to be breastfeeding while being exposed or having been exposed to study intervention (ie, environmental exposure). An example of environmental exposure during breastfeeding is a female family member or healthcare provider who reports that she is breastfeeding after having been exposed to the study intervention by ingestion.

The investigator must report exposure during breastfeeding to Pfizer Safety within 24 hours of the investigator's awareness, irrespective of whether an SAE has occurred. The information must be reported using the CT SAE Report Form. When exposure during breastfeeding occurs in the setting of environmental exposure, the exposure information does not pertain to the participant enrolled in the study, so the information is not recorded on a CRF. However, a copy of the completed CT SAE Report Form is maintained in the investigator site file.

An exposure during breastfeeding report is not created when a Pfizer drug specifically approved for use in breastfeeding women (eg, vitamins) is administered in accord with authorized use. However, if the infant experiences an SAE associated with such a drug, the SAE is reported together with the exposure during breastfeeding.

8.3.5.3. Occupational Exposure

The investigator must report any instance of occupational exposure to Pfizer Safety within 24 hours of the investigator's awareness using the CT SAE Report Form regardless of whether there is an associated SAE. Since the information about the occupational exposure does not pertain to a participant enrolled in the study, the information is not recorded on a CRF; however, a copy of the completed CT SAE Report Form must be maintained in the investigator site file.

8.3.6. Cardiovascular and Death Events

Not applicable.

8.3.7. Disease Related Events and/or -Disease Related Outcomes Not Qualifying as AEs or SAEs

Not applicable.

8.3.8. Adverse Events of Special Interest

Not applicable.

8.3.8.1. Lack of Efficacy

This section is not applicable because efficacy is not expected in the study population.

8.3.9. Medical Device Deficiencies

Not applicable.

8.3.10. Medication Errors

Medication errors may result from the administration or consumption of the study intervention by the wrong participant, or at the wrong time, or at the wrong dosage strength.

Exposures to the study intervention under study may occur in clinical trial settings, such as medication errors.

Safety Event	Recorded on the CRF	Reported on the CT SAE Report Form to Pfizer Safety Within 24 Hours of Awareness
Medication errors	All (regardless of whether associated with an AE)	Only if associated with an SAE

Medication errors include:

- Medication errors involving participant exposure to the study intervention;
- Potential medication errors or uses outside of what is foreseen in the protocol that do or do not involve the study participant.

Such medication errors occurring to a study participant are to be captured on the medication error page of the CRF, which is a specific version of the AE page.

In the event of a medication dosing error, the sponsor should be notified within 24 hours.

Whether or not the medication error is accompanied by an AE, as determined by the investigator, the medication error is recorded on the medication error page of the CRF and, if applicable, any associated AE(s), serious and nonserious, are recorded on the AE page of the CRF.

Medication errors should be reported to Pfizer Safety within 24 hours on a CT SAE Report Form **only when associated with an SAE**.

8.4. Pharmacokinetics and Pharmacodynamics

8.4.1. Pharmacokinetics

For the measurement of ritlecitinib concentrations, blood samples of 2 mL to provide approximately 0.5 mL of plasma will be collected into appropriately labeled tubes containing K₂EDTA (dipotassium ethylenediaminetetraacetic acid) at times specified in the **SoA**. Instructions for the collection and handling of biological samples will be provided in the laboratory manual or by the sponsor. The actual date and time (24-hour clock time) of each sample will be recorded.

The actual times may change, but the number of samples will remain the same. All efforts will be made to obtain the samples at the exact nominal time relative to dosing. Collection of samples up to and including 10 hours after dose administration that are obtained within 10% of the nominal time relative to dosing (eg, within 6 minutes of a 60-minute sample) will not be captured as a protocol deviation, as long as the exact time of the collection is noted on the source document and the CRF. Collection of samples more than 10 hours after dose administration that are obtained \leq 1 hour away from the nominal time relative to dosing will not be captured as a protocol deviation, as long as the exact time of the collection is noted on the source document and the CRF.

Samples will be used to evaluate the PK of ritlecitinib. Samples collected for analyses of ritlecitinib concentration may also be used to evaluate safety or efficacy aspects related to concerns arising during or after the study, for metabolite identification and/or evaluation of the bioanalytical method, or for other internal exploratory purposes.

Genetic analyses will not be performed on these plasma samples (unless consent for this was included in the informed consent). Participant confidentiality will be maintained.

Samples collected for measurement of plasma concentrations of ritlecitinib will be analyzed using a validated analytical method in compliance with applicable SOPs.

The PK samples must be processed and shipped as indicated in the instructions provided to the investigator site to maintain sample integrity. Any deviations from the PK sample handling procedure (eg, sample collection and processing steps, interim storage or shipping conditions), including any actions taken, must be documented and reported to the sponsor. On a case-by-case basis, the sponsor may make a determination as to whether sample integrity has been compromised.

8.4.2. Pharmacodynamics

The following samples for pharmacodynamics are required and will be collected from all participants in this study as specified in the [SoA](#):

- Target occupancy blood sample.

CCI

8.4.2.1. Target Occupancy:

Whole blood samples (approximately 30 mL) will be collected according to the timepoints specified in the [SoA](#) in sodium heparin tubes. PBMCs will be lysed and protein will be isolated. An ATP-competitive probe will be used to pull-down kinases that are not covalently bound to PF-06651600. Protein isolate will be digested with trypsin and unique peptides within JAK3, BMX, BTK, ITK, TEC and TXK have been identified and will be used to quantitate the amount of each kinase that is not occupied by ritlecitinib.

CCI

8.5. Genetics

[figure not shown]
8.5.1. Specified Genetics

Genetics (specified analyses) are not evaluated in this study.

8.5.2. Retained Research Samples for Genetics

A 4-mL blood sample optimized for DNA isolation Prep D1 will be collected according to the [SoA](#), as local regulations and IRBs/ECs allow.

CCI

See [Appendix 5](#) for information regarding genetic research. Details on processes for collection and shipment of these samples can be found in lab manual and other supporting documentation.

8.6. Biomarkers

Biomarkers evaluated in this study are detailed in [Section 8.4.2](#).

8.6.1. Retained Research Samples for Biomarkers

Retained Research Samples for biomarker analysis will not be collected in this study.

8.7. Immunogenicity Assessments

Immunogenicity assessments are not included in this study.

8.8. Health Economics

Health economics/medical resource utilization and health economics parameters are not evaluated in this study.

9. STATISTICAL CONSIDERATIONS

Detailed methodology for summary and statistical analyses of the data collected in this study is outlined here and further detailed in a SAP, which will be maintained by the sponsor. The SAP may modify what is outlined in the protocol where appropriate; however, any major modifications of the primary endpoint definitions or their analyses will also be reflected in a protocol amendment.

9.1. Statistical Hypotheses

No formal inferential statistics will be applied to the safety or PK data.

9.2. Analysis Sets

For purposes of analysis, the following analysis sets are defined:

Population	Description
Enrolled	All participants who sign the ICD.
Randomly assigned to investigational product	All participants who sign the ICD and meet all eligibility criteria.
Evaluable	The PK concentration population is defined as all participants enrolled and treated who have at least 1 concentration of ritlecitinib. The PD population is defined as all enrolled and treated who have at least 1 TO measurement.
Safety Analysis Set	All participants who take at least 1 dose of investigational product.

9.3. Statistical Analyses

The SAP will be developed and finalized before any analyses are performed and will describe the analyses and procedures for accounting for missing, unused, and spurious data. This section is a summary of the planned statistical analyses of the primary, secondary CCI endpoints.

9.3.1. Primary Endpoints

The primary endpoint in human PBMCs is TO of JAK3, BTK, ITK, RLK, TEC and BMX after a single dose of ritlecitinib. Target occupancy for each kinase at time t will be evaluated as follows:

$$\% \text{ Target Occupancy}_t = 100 \% - \% \text{ Free Target}_t$$

with TO_0 as the baseline variable of target occupancy, which is the mean of the two pre-dose measurements at Hour -1 and Hour 0 on Day 1. If only one of the two pre-dose measurements is available, TO_0 is the available pre-dose measurement.

TO profiles will be assessed graphically and summarized by nominal timepoints using descriptive statistics.

9.3.2. Secondary Endpoints

The secondary endpoints are pharmacokinetic parameters of ritlecitinib after single oral dose.

[figure not shown]
PK parameters will be derived, given available data, following single dose administration from the concentration-time profiles for ritlecitinib as follows:

Parameter	Definition	Method of Determination
AUC ₂₄	Area under the plasma concentration-time curve from time 0 to 24 hours	Linear/Log trapezoidal method
AUC _{last}	Area under the plasma concentration-time curve from time 0 to the time of the last quantifiable concentration (C _{last})	Linear/Log trapezoidal method
C _{av}	Average plasma concentration from time 0 to the time of the last quantifiable concentration	AUC ₂₄ /24
C _{max}	Maximum plasma observed concentration	Observed directly from data
C _{last}	Plasma concentration at 48 hours post-dose	Observed directly from data
T _{max}	Time to reach C _{max}	Observed directly from data as time of first occurrence

Concentrations will be assessed graphically. Concentrations (by nominal timepoints) and PK parameters will be summarized using descriptive statistics.

[figure not shown]

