The PK profile of ritlecitinib is characterized by rapid absorption median (T_{max} ranging from $\leq 0.75 - 1.5$ hour), rapid elimination ($t_{1/2}$ of ~ 2 hours) and are approximately dose proportional. Steady state generally appears to be reached by Day 4 for the QD regimens and Day 6 for the BID regimens based on similar median trough (predose) ritlecitinib beyond Day 6. Ritlecitinib has been evaluated at single oral doses ranging from 5 mg to 800 mg and multiple oral doses ranging from 50 mg to 400 mg QD and at 100 mg and 200 mg BID for 14 days. The clearance mechanisms for ritlecitinib in humans appear to be primarily by metabolism. Less than 10% of ritlecitinib is excreted unchanged in the urine.

In vitro and in vivo metabolite profiling suggested that the primary clearance mechanisms for ritlecitinib were both CYP450 mediated oxidation and glutathione related conjugation. Biliary excretion of ritlecitinib was limited in the rat and renal elimination was limited in humans. Reaction phenotyping in recombinant enzyme systems identified CYP3A4 as the predominant CYP450 isoform responsible for the metabolism of ritlecitinib, with minor contributions from CYP2C19 and CYP3A5.

CCI

Further information is available in the current version of the ritlecitinib IB.

Phase 2a Study in RA

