4.3. Justification for Dose

Single doses of 50 mg and 200 mg are being used in the study. A dose-ranging simulation using a pop-PK model for ritlecitinib⁴ showed that the proposed doses in healthy participants would provide, over the 48-hour collection interval, geometric mean C_{48} , C_{max} and C_{avg} concentration that encompasses those from clinical doses in patients with RA, UC, CD, AA or vitiligo (Table 3).

Table 3. Geometric mean C_{48} , C_{max} and C_{avg} for Healthy Participants and Patient Populations Under Evaluation

Population	Dose (mg)	C_{48} (ng/mL)	C_{max} (ng/mL)	C_{avg} (ng/mL)
Healthy	50	BQL	247.44	11.19
Healthy	200	BQL	1085.10	60.57
RA	100	BQL	482.60	51.21
UC	100	BQL	460.24	49.88
AA	50	BQL	256.59	17.07
Vitiligo	50	BQL	263.56	15.12

Based on prior Phase 1 data, 50 mg and 200 mg QD doses of ritlecitinib are expected to be safe and well tolerated in this study. A dose level of 200 mg QD ritlecitinib has demonstrated acceptable safety and tolerability for up to 14 days in healthy participants (B7981001), up to 4 weeks in participants with alopecia areata (B7931005) and up to 8 weeks in RA and UC participants (B7981006 and B7981005). The projected AUC_{48} and C_{max} of 2907 ng•h/mL and 1085 ng/mL at 200 mg single dose provides exposure margin of 3.2- and 2-fold, respectively from NOAEL observed in dogs in second 9-month toxicity study (Highest dose in dogs, 10 mg/kg/day; C_{max} (free) = 1910 ng/mL; $AUC_{24,ss}$ (free) = 7940 ng•h/mL; fu, dog = 0.82, fu, human=0.86).

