### 5.3. Methods to Manage Missing Data

For the analysis of safety endpoints, the sponsor data standard rules for imputation will be applied.

Methods to handle missing PK data are described below.

Concentrations Below the Limit of Quantification:

In all data presentations (except listings), concentrations below the limit of quantification (BLQ) will be set to zero. (In listings BLQ values will be reported as “<LLQ” where LLQ will be replaced with the value for the lower limit of quantification).

Deviations, Missing Concentrations and Anomalous Values:

In summary tables and plots of median profiles, statistics will be calculated having set concentrations to missing if 1 of the following cases is true:

1. A concentration has been collected as ND (ie, not done) or NS (ie, no sample),
2. A deviation in sampling time is of sufficient concern or a concentration has been flagged anomalous by the pharmacokineticist.

Note that summary statistics will not be presented at a particular time point if more than 50% of the data are missing.

Pharmacokinetic Parameters:

Actual PK sampling times will be used in the derivation of PK parameters. If a PK parameter cannot be derived from a subject's concentration data, the parameter will be coded as NC (ie, not calculated). (Note that NC values will not be generated beyond the day that a subject discontinues). In summary tables, statistics will be calculated by setting NC values to missing; and statistics will be presented for a particular dose with  $\geq 3$  evaluable measurements.

If an individual subject has a known biased estimate of a PK parameter (due for example to an unexpected event such as vomiting before all the compound is adequately absorbed from the gastrointestinal tract), this will be footnoted in summary tables and will not be included in the calculation of summary statistics or statistical analyses.

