**Table 3. PK Parameters to be Summarized Descriptively**

Parameter	Summary Statistics
AUC 24 , AUC last , C av , C max , C last	N, arithmetic mean, median, cv%, standard deviation, minimum, maximum, geometric mean and geometric cv%.
T max	N, median, minimum, maximum.

For the derivation of PK parameters, actual PK sampling times will be used.

To assess the relationship between the PK parameters and dose, AUC24, AUClast and Cmax will be plotted against dose (using a logarithmic scale), and will include individual subject values and the geometric means for each dose. Geometric means will have a different symbol than the individual values. These plots will be presented for both the dose-normalized (to a 1mg dose, by dividing the individual values and raw geometric means by dose) and non dose-normalized versions of these parameters.

Presentations for Ritlecitinib concentrations will include:

- A listing of all concentrations sorted by subject ID, dose and nominal time postdose. The concentration listing will also include the actual times. Deviations from the nominal time will be given in a separate listing.
- A summary of concentrations by dose and nominal time postdose, where the set of statistics will include n, mean, median, standard deviation, coefficient of variation (cv), minimum, maximum and the number of concentrations above the lower limit of quantification.
- Median concentrations time plots (on both linear and semi-log scales) against nominal time postdose by dose (all treatments on the same plot per scale, based on the summary of concentrations by dose and time postdose).
- Mean concentrations time plots (on both linear and semi-log scales) against nominal time postdose by dose (all treatments on the same plot per scale, based on the summary of concentrations by dose and time postdose).

- Individual concentration time plots by dose (on both linear and semi-log scales) against actual time postdose (there will be separate spaghetti plots for each dose per scale).
- Individual concentration time plots by subject (on both linear and semi-log scales) against actual time postdose [there will be separate plots for each subject (containing all doses) per scale].

For summary statistics, median and mean plots by sampling time, the nominal PK sampling time will be used, for individual subject plots by time, the actual PK sampling time will be used.

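### C_last is defined in two incompatible ways in the same PK table, and as the 48-hour concentration it cannot support the summary statistics the SAP requires

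*Protocol*

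**What the plan says.** The table in Protocol 9.3.2 and Table 2 in SAP 3.2.1 carry the same two rows. The C_last row reads "Plasma concentration at 48 hours post-dose", taken directly from the data. The AUC_last row ends the area at the "time of the last quantifiable concentration (C _{last})", so there C_last labels the last quantifiable value, whenever it occurs. Protocol Appendix 9 and SAP Appendix 2 give only the 48-hour meaning.

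Table 3 in Protocol 4.3 gives the simulated geometric mean C48, C_max and C_avg. The 200 mg row is "Healthy 200 BQL 1085.10 60.57", and the 50 mg row also shows BQL at 48 hours. Protocol 2.2.4 states a half-life of about 2 hours.

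SAP Table 3 names C_last among the parameters to be summarized by "N, arithmetic mean, median, cv%, standard deviation, minimum, maximum, geometric mean and geometric cv"%. SAP 5.3 contains two rules that could apply to a BLQ value:

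- The BLQ rule: "In all data presentations (except listings), concentrations below the limit of quantification (BLQ) will be set to zero".
- The rule for PK parameters that cannot be derived (NC): "In summary tables, statistics will be calculated by setting NC values to missing", with statistics shown for a dose only when at least 3 evaluable values exist.

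**The concern.** C_last is a named secondary endpoint with two meanings in one table. If the 48-hour sample is BLQ, as the protocol's own simulation projects, the two meanings select different samples. The SAP repeats the conflict rather than settling it.

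The 48-hour meaning also does not fit the planned summary. A parameter expected to be BLQ in most or all participants cannot carry geometric statistics, and the SAP does not say whether such a value counts as zero or as NC. Followed as written, the C_last row would be a set of zeros with some statistics undefined, or would not be presented. The reported C_last would also not be the concentration at which AUC_last ends.

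**Working it through.** **Inputs.** From Protocol Table 3: C_max 247.44 ng/mL and C_avg 11.19 ng/mL at 50 mg; C_max 1085.10 ng/mL and C_avg 60.57 ng/mL at 200 mg; C48 BQL at both. From Protocol 2.2.4: half-life about 2 h, median T_max 0.75 to 1.5 h. From Protocol 4.1: 8 participants per dose. The LLOQ and the between-subject variability are not given. I assume an LLOQ of 0.1 to 1 ng/mL and a lognormal half-life with median 2 h and CV 20% to 50%.

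**1. The plan's own figures.** C_avg × 48 = 60.57 × 48 = 2907.4 ng·h/mL, matching the stated AUC48 of 2907. For C48, take decay from C_max at 1 h, C(t) = C_max × 2^(−(t−1)/2):

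- 50 mg: 247.44 × 2^(−23.5) = 2.1 × 10⁻⁵ ng/mL
- 200 mg: 1085.10 × 2^(−23.5) = 9.1 × 10⁻⁵ ng/mL

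Moving T_max between 0.75 and 1.5 h gives 1.9 to 2.5 × 10⁻⁵ and 8.4 × 10⁻⁵ to 1.1 × 10⁻⁴. Both doses are far below any LLOQ in the assumed range, in agreement with the BQL entries.

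**2. Is 2 h consistent with the simulated exposures?** Effective half-life ≈ (C_avg × 48 / C_max) × ln 2:

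- 50 mg: 537.1/247.44 × 0.693 = 1.5 h
- 200 mg: 2907.4/1085.10 × 0.693 = 1.9 h

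Neither suggests a longer effective half-life.

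**3. Half-life needed for a quantifiable 48-hour sample.** Required half-life = 47 × ln 2 / ln(C_max/LLOQ).

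| LLOQ (ng/mL) | 50 mg | 200 mg |
|---|---|---|
| 0.1 | 4.17 h | 3.51 h |
| 0.5 | 5.25 h | 4.24 h |
| 1 | 5.91 h | 4.66 h |

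**4. Chance of quantifiable values among 8.** Per participant, p = P(half-life exceeds the required value), with log-scale SD √ln(1 + CV²). The binomial distribution then gives the counts.

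| Scenario | Quantity | 50 mg | 200 mg |
|---|---|---|---|
| CV 20%, LLOQ 1 | P(≥1 of 8) | <0.001 | <0.001 |
| CV 30%, LLOQ 0.5 | P(≥1 of 8) | 0.004 | 0.041 |
| CV 50%, LLOQ 0.1 | p per participant | 0.060 | 0.117 |
| CV 50%, LLOQ 0.1 | P(≥1 of 8) | 0.39 | 0.63 |
| CV 50%, LLOQ 0.1 | P(≥3 of 8) | 0.010 | 0.057 |

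**5. The SAP Table 3 statistics under each rule.**

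- *BLQ = 0, all eight BLQ:* mean, median, SD, minimum and maximum are all 0, and cv% is 0/0. The geometric mean requires log(0), and geometric cv% has no value.
- *BLQ = 0, one quantifiable value c and seven zeros:* mean = c/8 and SD = c/√8, so cv = √8 = 283% whatever c is. The geometric statistics still fail.
- *BLQ treated as NC:* the row appears only with 3 or more evaluable values, which by step 4 has probability at most about 1% (50 mg) or 6% (200 mg).

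**6. Which sample each definition selects.** At a 2 h half-life and LLOQ 0.1 to 1 ng/mL, concentrations stay quantifiable until about 17 to 24 h at 50 mg and 21 to 28 h at 200 mg. The late sampling times in Protocol Table 2 are 8, 24 and 48 h. The last quantifiable scheduled sample is therefore at 8 h or 24 h, not 48 h.

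**The case against.** The strongest case on the other side is that this is a labelling slip with little consequence.

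- **Impact.** No inference rests on C_last, and AUC_last is defined by the time of the last quantifiable sample, so its value does not depend on the C_last label. This stands and limits the weight of the point.
- **Simple statistics survive.** Under the zero rule N, mean, median, SD, minimum and maximum all compute, and cv% is undefined only if every value in the arm is BLQ. This also stands. The geometric mean can be called zero rather than undefined if taken as a product, but geometric cv% has no value either way. A row of zeros with cv% of 0/0 or 283% tells the reader nothing beyond the count above LLOQ.
- **The zero rule is the natural reading.** An observed BLQ result is not a parameter that cannot be derived. That is a fair reading, but the SAP does not state it, and it is the reading under which the geometric statistics fail.
- **The quantities are assumed.** The LLOQ, the half-life CV and the lognormal form are mine. The exposure check in step 2 is dominated by the early hours and cannot exclude a small slow terminal phase. Table 3 gives a geometric mean, so BLQ in most or all participants is an inference. The argument itself needs only the protocol's BQL projection; the calculations show how far it extends.
- **The conflict could be settled the other way.** Deleting the label from the AUC_last row and keeping C_last at 48 h would remove the contradiction. It would leave a parameter with no usable geometric summary. It is true that a last-quantifiable C_last mixes sampling times: on this model the 8 h and 24 h values differ by 2⁸ = 256-fold (about 22 against 0.09 ng/mL at 50 mg). Its summary should be read with that in mind.

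**Conclusion.** The concern holds. The contradiction is in the text and needs no assumption. Given the BQL projections at both doses, the cv% and geometric statistics required for C_last would be undefined, uninformative or not presented. Across the assumed ranges, the chance of any quantifiable 48-hour value among 8 runs from below 1% to 39% at 50 mg and from below 1% to 63% at 200 mg. Even the upper ends do not rescue the geometric statistics under the zero rule.

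This should be corrected, but its reach is small: one descriptive secondary PK parameter. Target occupancy, C_max, T_max, AUC24 and AUC_last are unaffected, and AUC_last can still be checked against the planned concentration listings and individual plots.

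**What to change.** Define C_last as the last quantifiable concentration, in line with the AUC_last row, in Protocol 9.3.2, SAP Table 2 and both abbreviation lists. It is then positive for every participant with any quantifiable sample, so the SAP Table 3 statistics can be computed, subject to the 3-value minimum. Adding T_last is optional, but it would show which sampling time each value comes from.

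No separate 48-hour parameter is needed. The by-timepoint concentration summary in SAP 6.2.1 already covers 48 h and includes "the number of concentrations above the lower limit of quantification". If a 48-hour parameter is kept, name it C48, state whether a BLQ value is zero or NC, and drop its geometric statistics.

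The cost is one table row and one abbreviation entry in each document, with no new data. Protocol Section 9 allows the SAP to modify what the protocol outlines, and requires an amendment only for major changes to the primary endpoints or their analyses. The SAP correction can therefore be made first and the protocol aligned at the next amendment.
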